3.2 Secondary Objectives

• To assess the efficacy of B244 versus vehicle by the change in Atopic Dermatitis Area Severity Index (EASI) Score from Baseline to post-baseline visits

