15.4.5 Efficacy Analyses

All efficacy analyses will be performed on the ITT population and PP population. P-values from analyses of efficacy endpoints must be interpreted in an exploratory fashion since there is no adjustment for multiple endpoints in this study.

The EASI score and other continuous efficacy endpoints will be summarized using descriptive statistics at Baseline, Day 14, Day 28 and Day 42 for actual values and change-from-baseline values. The difference in treatment groups in change-from-baseline values at post-baseline visits will be analyzed using a mixed Analysis of Variance with one between-subject variable (active group vs. vehicle group) and one within-subject variable (Baseline vs. Day 14, Day 28, Day 42). The interaction between within-subject and between-subject variable will be included in the mixed model to test if any difference in treatment groups at post-baseline visits. Outputs from the analysis will include the p-value for the treatment group and interaction factor separately. The p-value should be evaluated at a significance level of 0.05.

Additionally, a one-sided two-sample equal-variance t-test will be performed as a supportive test to analyze the differences in treatment group means in change from baseline at each post-baseline visit (Day 14, Day 28, Day 42). Output from the analysis will include a 95% confidence interval for the difference in treatment groups means at each visit, and the p-values from the hypothesis test of no difference in treatment group means at each visit. The p-value should be evaluated at a one-sided significance level of 0.025.

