### 1.1.2.2. Secondary Objectives

▼ To assess the efficacy of B244 versus vehicle by the change in Atopic Dermatitis Area Severity Index (EASI) Score from baseline to post-baseline visits.

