#### 4.3.1. EASI, IGA, VAS

EASI, IGA, and VAS scores will be summarized using descriptive statistics at Baseline, Day 14, Day 28, and Day 42 for actual values and change-from-baseline values. Tabulations will be produced for both the ITT and PP populations.

The difference in treatment groups in change-from-baseline values at post-baseline visits will be analyzed using a mixed model Analysis of Variance with one between-subject variable (active group vs. vehicle group) and one within-subject variable (Day 14, Day 28, and Day 42).

The interaction between within-subject and between-subject variable will be included in the mixed model to test if any difference in treatment groups at post-baseline visits.

The model will include treatment group, siteid and visit as the independent effects and the interaction term treatment group\*visit\*siteid. Outputs from the analysis will include the p-value

for the treatment group and interaction factor separately. The p-value should be evaluated at a significance level of 0.05.

Mixed model ANOVA will be implemented using PROC GLM in SAS using the REPEATED option.

Additionally, a one-sided two-sample equal-variance t-test will be performed as a supportive test to analyze the differences in mean change in scores from baseline between treatment groups at each post baseline visit (Day 14, Day 28, Day 42). Output from the analysis will include a one sided 95% confidence interval and p-value. The p-value should be evaluated at a one-sided significance level of 0.025.

The above analysis will also be performed by subgroups – age, gender, and race for the ITT Population.

An exploratory analysis will also be conducted by the number of AD sites (1, 2 and >2) the subjects had.

At each visit, based on the score, subjects will be categorized into the below categories.

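### SAP 4.3.1 names two different interactions for the EASI model, and the reported interaction and per-visit p-value are not tied to the powered Day 28 comparison

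*SAP*

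**What the plan says.** **Objective and endpoint.** Both documents give the secondary objective as the change in "Atopic Dermatitis Area Severity Index (EASI) Score from Baseline to post-baseline visits" (protocol 3.2; SAP 1.1.2.2 has the same words). Protocol 4.2 fixes the EASI endpoint at Day 28, and protocol 15.1 powers the Day 28 change. SAP 1.2.4.1 gives the EASI endpoint without a time point.

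**Protocol model (15.4.5).** A mixed ANOVA with treatment as the between-subject factor, a within-subject factor whose levels include Baseline as well as Days 14, 28 and 42, and their interaction. There is no site term. "Outputs from the analysis will include the p-value for the treatment group and interaction factor separately". In addition, "a one-sided two-sample equal-variance t-test will be performed as a supportive test to analyze the differences in treatment group means" at each visit.

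**SAP model (4.3.1).** The within-subject factor has three levels, Days 14, 28 and 42. One paragraph says: "The interaction between within-subject and between-subject variable will be included in the mixed model to test if any difference in treatment groups" at the post-baseline visits. The next says: "The model will include treatment group, siteid and visit as the independent effects and the interaction term treatment group", and the term continues with visit and siteid. p-values are again requested for treatment and for the interaction, at 0.05. The software line reads: "Mixed model ANOVA will be implemented using PROC GLM in SAS using the REPEATED option".

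**Related text.** SAP 3.6 says that no analyses adjusting for covariates are planned. SAP section 5 lists the per-protocol definition and the postponed biomarker and microbial analyses, and nothing about the model. Table 14.2.1.1 prints a p-value [1], footnoted only as coming from the mixed model, in the change block of each visit.

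**The concern.** Two adjacent paragraphs of SAP 4.3.1 describe different interactions, and the requested output is simply the interaction p-value. One candidate, treatment × visit, asks whether the treatment difference varies over the visits. The other, treatment × visit × site, asks whether that pattern differs between sites, or something broader if the lower-order terms are left out. Neither is the question the trial was sized to answer, which is whether the arms differ at Day 28. The remaining model output, the treatment p-value, averages Days 14, 28 and 42, and Day 42 falls two weeks after treatment ends.

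The practical risk is that two programmers fit different models and print different quantities as p-value [1]. The visit-wise summary shells for EASI, VAS, IGA and Skindex 16 share this footnote: 14.2.1.1–6, 14.2.3.1–6, 14.2.5.1–6 and 14.2.8.1–6, so 4 × 6 = 24 tables. A significant interaction could also be read as efficacy when it reflects differences between sites. No rule says which result governs if the treatment p-value and the Day 28 t-test disagree.

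**Working it through.** **Inputs from the documents.** Protocol 15.1: Day 28 difference (−1.4) − (−5.3) = 3.9, SD 7.0, 52 per arm, one-sided alpha 0.025. SAP 4.3.1: three post-baseline visits.

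**Assumptions (not in the documents).** Number of sites S, correlation ρ between changes at different visits, SD 7.0 at every visit, and the size of the effect at Days 14 and 42.

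**1. The plan's own figure.** Noncentrality = 3.9 / (7.0 × √(2/52)) = 3.9 / 1.373 = 2.841. With 102 df, power is 80.3%, which reproduces the stated figure of more than 80%.

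**2. The three-way term.** Two arms × S sites × 3 visits give 6S cell means. The intercept and main effects use 1 + 1 + (S − 1) + 2 = S + 3.
- *Literal reading* (main effects plus the three-way term only): 6S − (S + 3) = 5S − 3 df. That is 22, 37 and 62 for 5, 8 and 13 sites. These df pool treatment × site (S − 1), treatment × visit (2), visit × site (2(S − 1)) and the three-way part.
- *Full factorial*: the two-way terms take (S − 1) + 2 + 2(S − 1) = 3S − 1, leaving 2(S − 1) df, or 8, 14 and 24. A benefit that is the same at every site lies wholly in the lower-order terms. Noncentrality is 0 and rejection is 5% for any size or visit pattern of that benefit.
- On the literal reading, a constant 3.9-point benefit also gives noncentrality 0. A 1.95 / 3.9 / 1.95 pattern over Days 14 / 28 / 42 gives 10.2% rejection (simulated, 5 sites, 10 per arm per site, ρ = 0.5). With no treatment effect but site × visit variation of SD 2 points (assumed), the same simulation rejects 77.9% of the time.

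**3. Software.** In PROC GLM with REPEATED, visit is a dimension of the response, not a model term, and it is crossed with every between-subject term. Visit × treatment appears whenever treatment is in the model. The three-way term appears only if treatment × site is added. The model sentence cannot be entered as written.

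**4. Treatment × visit, with and without Baseline.**
- *SAP, three levels, constant benefit*: every visit equals the mean effect, so noncentrality is 0 and power is 5%. For 1.95 / 3.9 / 1.95, power is 22% to 45% (ρ 0.3 to 0.7).
- *Protocol, four levels including Baseline*: using actual scores and compound symmetry, the effects are 0, 3.9, 3.9, 3.9 with mean 2.925. The sum of squared deviations is 2.925² + 3 × 0.975² = 11.41. A change SD of 7.0 implies a within-subject variance of 49 / 2 = 24.5. Noncentrality = 26 × 11.41 / 24.5 = 12.11. With 3 and 306 df, power is about 84%.

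**5. Treatment p-value (visit average).** Effect = 3.9 × (d14 + 1 + d42) / 3, where d14 and d42 are the Day 14 and Day 42 effects as fractions of the Day 28 effect. SD = 7.0 × √((1 + 2ρ)/3), which is 5.42, 5.99 and 6.52 at ρ = 0.4, 0.6 and 0.8.

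| Day 14 / 28 / 42 effect, as fraction of 3.9 | ρ = 0.4 | ρ = 0.6 | ρ = 0.8 |
|---|---|---|---|
| 1 / 1 / 1 | 95.3% | 90.8% | 85.6% |
| 0.8 / 1 / 0.8 | 88.3% | 81.3% | 74.5% |
| 0.5 / 1 / 1 | 85.7% | 78.2% | 71.2% |
| 0.5 / 1 / 0.5 | 67.8% | 59.1% | 52.2% |
| 0.5 / 1 / 0 | 44.3% | 37.6% | 32.7% |

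The Day 28 test stays at 80.3% in every row.

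**The case against.** The best defence is that the two sentences can be read together. Both describe terms to be included, and the named procedure yields visit × treatment anyway. The t-test at Day 28 is fully specified and is the test that was powered. The protocol says "P-values from analyses of efficacy endpoints must be interpreted in an exploratory fashion", and the primary objective is safety. The visit-averaged treatment p-value matches the post-baseline objective, gains power if the effect is stable, and comes from the protocol, as does the supportive rank of the t-test.

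Most of this stands, and it rules out several stronger conclusions that a reader might draw:
- *That the three-way term carries no treatment information on any reading.* On the literal reading it contains the 2 df of treatment × visit. It cannot isolate a benefit common to all sites, which is a narrower statement.
- *That no model-based Day 28 test is foreseen.* Table 14.2.1.1 is repeated for all visits, so a slot for a mixed-model p-value at Day 28 exists. What is missing is the definition of the effect it tests.
- *That treatment × visit is missing from the analysis.* PROC GLM with REPEATED would produce it. What is unclear is which interaction is reported.
- *That the SAP simply repeats the protocol's interaction in its first paragraph.* The protocol's factor includes Baseline and the SAP's does not, which changes what the interaction can detect.

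The defence does not settle which interaction is reported or what p-value [1] means, and it does not account for the unlisted changes. Exploratory status lowers the stakes, but the model must still be reproducible, and SAP 3.2 promises formal testing of the efficacy endpoints.

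**Conclusion.** The point holds as a specification fault that should be fixed, with high confidence in the textual part. SAP 4.3.1 names two interactions. The three-way term cannot isolate a benefit common to all sites, and treatment × visit on the SAP's three levels has 5% power for a constant benefit. The treatment p-value is not the Day 28 comparison: for the same Day 28 effect its power runs from 33% to 95% over the assumed patterns and correlations, against 80.3% for the Day 28 test. That range shows both gain and loss; it does not show a bias in a known direction.

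The site term, the three-way interaction and the dropped Baseline level are departures from protocol 15.4.5 that SAP section 5 does not list, and the site term sits uneasily with SAP 3.6. The effect is confined to how a secondary endpoint, and the exploratory endpoints that share its model, are read. All figures other than the 80.3% and the degree-of-freedom formulas rest on the stated assumptions about sites, correlations and effect patterns.

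**What to change.** - In SAP 4.3.1, replace treatment × visit × site with treatment × visit and keep site as a main effect only. If PROC GLM with REPEATED is retained, visit × site will be fitted as well because site is in the model; say that it is not a reported test.
- Define p-value [1] in Table 14.2.1.1 and the shells that share it as the by-visit treatment contrast from that model, reported with a confidence interval. Restoring treatment × visit alone is not enough, because of its 5% power for a constant benefit.
- Name the Day 28 contrast, or the already planned and powered Day 28 t-test, as the EASI result that is read first.
- Restore Day 28 in the EASI endpoint of SAP 1.2.4.1 and reconcile SAP 3.6 with the site term.
- List in SAP section 5 the site term, the interaction, the dropped Baseline level and the changed rank of the Day 28 test. The last is itself a departure from protocol 15.4.5, where the t-test is supportive.

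A baseline EASI covariate is optional and not part of the error.

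The cost is SAP wording and minor programming, with no new data. The drawback is power: if the effect is constant over visits, the Day 28 test has 80% power against 86% to 95% for the visit-averaged test (assumed correlations 0.8 to 0.4).

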13.3 Study Completion

A completed participant is one who has completed all study visits. Day 42 study visit is defined as the participant's last visit.

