### 1.2. Study Design

### 1.2.1. Synopsis of Study Design

This is a prospective, vehicle controlled, double blind, multicenter, randomized Phase II trial comparing the effect of twice daily B244 application for 28 days versus vehicle application on treatment of mild to moderate AD.

Subjects who have clinically confirmed diagnosis of mild to moderate AD are eligible for enrollment. Subjects must be in general good health as determined by a thorough medical history, physical examination, and vital signs.

It is estimated that approximately 130 subjects will be randomized in order to provide 104 subjects for inclusion in the primary analysis, assuming a 20% drop-out rate.

After screening and recruitment, subjects will be randomized 1:1 to B244 or vehicle application for 28 days. Subjects will apply a total of 8 pumps of investigational product (IP) per application to all affected areas twice-a-day for 28 days.

[figure not shown]
Clinical assessments of response to treatment will be made at Baseline, Study Days 14 and 28. Subject will come back for the final visit on Study Day 42.

Safety evaluations will consist of review of subject's medical history at screening and on-going assessment of adverse events reported throughout the study duration.

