### 2. SUBJECT POPULATION

### 2.1. Population Definitions

The following subject populations will be evaluated and used for presentation and analysis of the data:

- x Intent-to-Treat (ITT) Population: Includes all randomized subjects. Subjects will be analyzed according to the treatment assigned by the randomization schedule. The ITT population will be the primary population for efficacy analyses.
- x Safety Population: Includes all subjects who received at least 1 dose of study medication. Subjects will be analyzed according to the study drug received.
- Per Protocol (PP) Population: Includes subjects who administered at least 50% of IP, have at least one baseline and post baseline Day 28 visit and did not have any major protocol violations. The PP population will be used for supportive summaries of efficacy data.

The ITT population is the primary population for the analysis of efficacy parameters. A subset of efficacy parameters will be evaluated for the PP population (see Section 4.3). The Safety population is the primary population for the analysis of safety endpoints.

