### 3.6. Adjustments for Covariates

No formal statistical analyses that adjust for possible covariate effects are planned.

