### Table 14.2.1.1

Summary of Values and Change from Baseline for EASI Score (ITT Population)

Visit	Actual/ Change	Statistic	B244 (N=xx)	Placebo (N=xx)	Overall (N=xx)
Baseline	Actual	n	XX	XX	xx
		Mean (SD)	xx.x (xx.xx)	xx.x (xx.xx)	xx.x (xx.xx)
		Median	XX.X	XX.X	xx.x
		Min, Max	xx, xx	XX, XX	XX, XX
Day 14	Actual	n	XX	XX	XX
		Mean (SD)	xx.x (xx.xx)	xx.x (xx.xx)	xx.x (xx.xx)
		Median	XX.X	XX.X	XX.X
		Min, Max	xx, xx	XX, XX	xx, xx
	Change	n	XX	XX	xx
		Mean (SD)	xx.x (xx.xx)	xx.x (xx.xx)	xx.x (xx.xx)
		Median	XX.X	XX.X	XX.X
		Min, Max	XX, XX	xx, xx	xx, xx
		p-value [1]	x.xxxx		
		p-value [2]	x.xxx		
		95% CI [2]	xx.xx, xx.xx		

 p-value is from Mixed model ANOVA.

Source: ZLMWLQQQ

Programming Note: Repeat for all visits

Repeat Table 14.2.1.1 for the following tables:

```
Table 14.2.1.2 Summary of Values and Change from Baseline for EASI Score (PP Population)
Table 14.2.1.3 Summary of Values and Change from Baseline for EASI Score by Gender (ITT Population)
Table 14.2.1.4 Summary of Values and Change from Baseline for EASI Score by Age Category (ITT Population)
Table 14.2.1.5 Summary of Values and Change from Baseline for EASI Score by Race (ITT Population)
Table 14.2.1.6 Summary of Values and Change from Baseline for EASI score by Number of Atopic Dermatitis Sites (ITT Population)
```

 p-value is from t- test.

Confidential

Page 1 of x

DATE: HH:MM/DDMMMYYYY

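### SAP 4.3.1's repeated-measures efficacy test is labelled ITT but uses only subjects observed at Day 14, 28 and 42, and its listed effects match neither the procedure nor the hypothesis it states

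*SAP*

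**What the plan says.** SAP 4.3.1 analyses change from baseline with treatment as the one between-subject variable and visit (Day 14, 28, 42) as the one within-subject variable. It then says "The interaction between within-subject and between-subject variable will be included in the mixed model to test if any difference in treatment groups" at the post-baseline visits. The next paragraph says "The model will include treatment group, siteid and visit as the independent effects and the interaction term", and the only interaction it names is `treatment group*visit*siteid`. The software instruction is "Mixed model ANOVA will be implemented using PROC GLM in SAS using the REPEATED option". One treatment p-value and one interaction p-value are to be reported, at 0.05. The same analysis is repeated by age, gender and race, and SAP 4.3.2 applies a similar model to Skindex-16. One-sided t-tests at each visit are called supportive.

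Around this:

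- SAP 2.1 defines ITT, the primary efficacy population: "Includes all randomized subjects. Subjects will be analyzed according to the treatment assigned by the randomization schedule".
- SAP 3.10 and Protocol 15.4.6 rule out imputation. SAP 1.2.2 keeps withdrawn subjects' data evaluable up to withdrawal.
- SAP 3.6 says "No formal statistical analyses that adjust for possible covariate effects are planned". SAP section 5 does not list a site term as a change.
- Protocol 15.4.5 has no site term, and its within-subject factor includes Baseline as a level.
- The Table 14.2.1.1 shell repeats, for every post-baseline visit, a result footnoted "p-value is from Mixed model ANOVA".
- On numbers, SAP 1.2.1 says "approximately 130 subjects will be randomized in order to provide 104 subjects for inclusion in the primary analysis", and Protocol 13.3 says "A completed participant is one who has completed all study visits".

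**The concern.** Three things do not fit together.

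1. **Population.** `REPEATED` in PROC GLM takes the three visits as three dependent variables in one row per subject, and a row with any of them missing is dropped. This is a standard property of the procedure, not a statement in the documents. Without imputation, the test labelled ITT is a complete-case test. It discards observed values from withdrawn subjects and from subjects who miss only one visit.
2. **Effects.** In that layout visit is the `REPEATED` factor, so neither visit nor `treatment group*visit*siteid` can be typed as a `MODEL` term. Treatment-by-visit is described but not listed. Site is listed although SAP 3.6 plans no adjustment.
3. **Hypothesis.** SAP 4.3.1 offers the interaction as the test of any post-baseline treatment difference. Once Baseline is no longer a level, it does not test that.

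At stake are the p-values named first for the efficacy comparison: which subjects they rest on, and what they mean.

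**Working it through.** **The plan's own figure.** Inputs from Protocol 15.1: difference (−1.4) − (−5.3) = 3.9, SD 7.0, one-sided 0.025, 52 per arm. The noncentral t gives power 0.8035, and 104 / 0.8 = 130. Both stated figures reproduce.

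**Subjects used.** 130 × 0.20 = 26 lost, leaving 104. Completers are those with all visits, so at most 104 of 130 (80%) enter PROC GLM with `REPEATED`.

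**Observed values discarded.** The 104 completers supply 104 × 3 = 312 values. The documents do not give dropout timing, so three assumed patterns are shown, all with Day 14 observed:

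| Pattern of the 26 losses | Discarded | Total observed | Share |
|---|---|---|---|
| All leave after Day 14 | 26 | 338 | 8% |
| Half miss only Day 42 | 13×2 + 13 = 39 | 351 | 11% |
| All miss only Day 42 | 26×2 = 52 | 364 | 14% |

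**Power of the model's treatment test.** Monte Carlo, 2000 trials per setting (error about 0.01), 65 per arm, SD 7, no site effect. Assumed mean changes at Day 14/28/42 are −3.35/−5.3/−4.0 (active) and −1.4/−1.4/−1.4 (vehicle); only the Day 28 values come from the plan. Assumed correlation between visits is 0.5 or 0.7. Ranges run over correlation and the three patterns above:

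| Dropout | Complete-case | Likelihood | Loss |
|---|---|---|---|
| Unrelated to outcome | 0.61–0.71 | 0.68–0.80 | 5–10 points |
| Related to Day 14 change (logistic slope 0.2) | 0.59–0.70 | 0.71–0.79 | 8–12 points |

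The likelihood test here was a Wald t with 120 df, unstructured covariance. Under the null (half missing only Day 42) the false-positive rates, complete-case/likelihood, were 0.062/0.058 and 0.050/0.051.

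Analytic check of the complete-case column: the mean difference over visits is (1.95 + 3.9 + 2.6)/3 = 2.82. The SD of a three-visit mean is 7√((1+2ρ)/3) = 5.7 at ρ = 0.5 and 6.3 at ρ = 0.7. At 52 per arm, power is about 0.70 and 0.62.

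**Shift in the Day 28 difference** (true value 3.9; complete-case against all subjects observed at Day 28):

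- Dropout unrelated to outcome: none.
- Related to Day 14 change, half missing only Day 42: 3.70 against 3.80 and 3.67 against 3.83, a shift of 0.10 to 0.16.
- Related to Day 14 change, all missing only Day 42: 3.71 against 3.88 and 3.63 against 3.89, a shift of 0.17 to 0.26.

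Every shift is toward zero effect, against a standard error of about 1.3.

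**The effect list.** The nearest model that runs puts treatment, siteid and treatment-by-site in `MODEL`, with visit as the `REPEATED` factor. It yields treatment-by-visit and the three-way term, but also treatment-by-site and visit-by-site, which the SAP does not list. It still deletes incomplete subjects.

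**The interaction.** Write the treatment difference in change at the three visits as d14, d28, d42. The SAP's treatment-by-visit term (2 df) tests d14 = d28 = d42. A constant benefit of 3.9 at every visit satisfies that exactly, so the term shows nothing. With Baseline as a level, as in Protocol 15.4.5, the change there is zero in both arms, so no interaction would mean d14 = d28 = d42 = 0, which is the stated hypothesis. Dropping Baseline changed the question but not the description.

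**The case against.** **The model can be run.** A reader might infer from the mismatched effect list that no analysis is possible. That goes too far: the list can be read as describing the model rather than as SAS syntax, and the nearby `REPEATED` model runs and does test treatment-by-visit. PROC GLM also prints a separate ANOVA for each visit, a possible source for the per-visit shell p-value. This stands. What remains is that the SAP does not specify that model, the shell does not say which p-value it prints, and deletion is unchanged.

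**Inflated error.** A reader might infer that, with one row per visit, a subject's visits would be treated as independent. The standard error would then be too small by √(1+2ρ) = 1.41 to 1.55, and a nominal 0.05 would become about 0.17 to 0.21. The SAP rules this out by naming the `REPEATED` option.

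**The trial is sized for 104.** True: the t-test power is not broken. Nor should the simulated 0.59 to 0.71 be set against the plan's 80%. It concerns a different test and reflects the smaller effects assumed at Day 14 and Day 42. Only the gap between the two methods bears on this point.

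**Little harm.** Safety is the primary objective (Protocol 3.1), and Protocol 15.4.5 calls efficacy p-values exploratory. The descriptives, t-tests and their intervals, shift tables and improvement tests can all use available cases. This stands and limits the weight of the point.

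**Bias in favour of B244.** Protocol 8.14 discontinues subjects who need rescue, so outcome-related loss is plausible, and a reader might infer a favourable bias. The documents give no rescue rate or dropout timing, and the simulated deletion shifts all go the other way. Bias from missing Day 28 values would affect the t-test as well and is not claimed here.

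**Conclusion.** The point holds and should be fixed, but it does not threaten the primary objective. Three parts rest on the documents and the standard behaviour of PROC GLM:

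- The first-named efficacy test is a complete-case test under an ITT label, with at most 104 of 130 subjects at the planned loss.
- Its effect list matches neither the procedure nor the surrounding text, and its site term is unrecorded and conflicts with SAP 3.6.
- Its interaction does not test the hypothesis stated for it.

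The sizes are conditional. The 8 to 14% of values discarded depends on assumed dropout timing. The 5 to 12 points of power also depend on the assumed Day 14 and Day 42 means, the correlation and the dropout mechanism. Validity under the null is not in question in the simulated settings, and the shift of 0 to about 0.26 EASI points is small and conservative.

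**What to change.** In SAP 4.3.1, and by reference 4.3.2:

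- Replace PROC GLM with a likelihood-based repeated-measures model: PROC MIXED, one row per visit, `REPEATED visit / SUBJECT=subject TYPE=UN`, Kenward-Roger degrees of freedom.
- Fit treatment, visit, treatment-by-visit and siteid as fixed effects. Drop the three-way term.
- Use every value recorded at Day 14, 28 or 42 from randomized subjects. Early Termination values stay outside unless SAP 3.11 is given a rule assigning them to a visit.
- Test any post-baseline difference by the treatment effect averaged over visits, or by the joint test of the three visit contrasts; name one in advance. Label treatment-by-visit as the test of whether the effect varies over visits.
- In the shells, print the model's treatment contrast at each visit, the Day 28 contrast with a two-sided 95% confidence interval (which matches one-sided 0.025), and the number of subjects contributing.
- Record the site term and the departure from Protocol 15.4.5 in SAP 3.6 and section 5.

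The three-visit GLM result may be kept as a labelled complete-case sensitivity analysis.

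The cost is SAP wording, edits to the Table 14.2.1, 14.2.3, 14.2.5 and 14.2.8 series, and some reprogramming. It needs no new data, visits or subjects, and the no-imputation rule stands.

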5 STUDY DESIGN

- This is a Prospective, Vehicle Controlled, Double Blind, Multicenter, Randomized Phase II trial, comparing the effect of twice daily B244 application for 28 days vs vehicle application on treatment of mild to moderate AD
- We will enroll approximately 130 patients and complete 104 patients
- After screening and recruitment, participants will be randomized to active or vehicle application for 28 days.
- Subjects will apply a total of 8pumps of IP per application to all affected areas twice-a-day (i.e. 8pumps in the morning and 8pumps again at night) for 28 days.
- Subjects will be provided with cleanser and moisturizer to use for the duration of the study
- Randomization will be 1:1 so that equal number of patients will be treated in each Arm of the study.
- All B244 randomized subjects will be treated at the dose of 4x10⁹ cfu/ml
- Screening will occur at Days -21 to -14
- Washout will occur after Screening visit (Days -14 to -1)
- Randomization will occur during the baseline period for the study
- Clinical assessments of response to treatment will be made at Baseline, Study Days 14 and 28.
- Subject will come back for the final visit on Study Day 42
- Safety evaluations will consist of review of participant's medical history at screening and on-going assessment of adverse events reported throughout the study duration.

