15 STATISTICAL CONSIDERATIONS

15.1 Sample Size

A total sample size of 130 randomized subjects, allows for a dropout rate of 20%.

A sample size of 52 per group achieves >80% power to reject the null hypothesis of equal means when the population mean difference is $\mu 1 - \mu 2 = (-1.4) - (-5.3) = 3.9$ with a standard deviation for both groups of 7.0 and with a significance level (alpha) of 0.025 using a one-sided two-sample equal-variance t-test.

The power calculation assumes baseline treatment group means of 14 in EASI score. The change from baseline to Day 28 is assumed to be -1.4 for the vehicle group and -5.3 for the active group; this represents about 38% reduction in EASI score for the active group and 10% reduction in EASI score for the placebo group.

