### 3.8. Subpopulations

EASI, IGA, VAS, and Skindex 16 Scores will be reported separately for Black versus Non Black subjects, subjects  $\geq$  30 years versus < 30 years and male vs female subjects. Some of the parameters will also be presented by number of atopic dermatitis sites.

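### Efficacy is tested separately within each sex, age, race and AD-site group with no treatment-by-subgroup interaction, so discordant significance can easily be misread as differential efficacy

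*SAP*

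**What the plan says.** SAP 4.3.1 sets out a repeated-measures ANOVA of change from baseline, plus a supportive one-sided t-test at Days 14, 28 and 42 judged at 0.025. It then states: "The above analysis will also be performed by subgroups", naming age, gender and race in the ITT population. SAP 3.8 gives the race split and the manner of reporting: "EASI, IGA, VAS, and Skindex 16 Scores will be reported separately for Black versus Non Black subjects". It also splits at age 30 and by sex. SAP 4.3.2 extends the subgroup analyses to Skindex 16.

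A further sentence in SAP 4.3.1 adds the fourth factor: "An exploratory analysis will also be conducted by the number of AD sites (1, 2 and >2) the subjects had". That sentence names no test. The p-values come from the shells: Tables 14.2.1.3 to 14.2.1.6 (EASI by gender, age, race and number of AD sites) all repeat Table 14.2.1.1, which carries a mixed-model p-value, a t-test p-value and a 95% CI. The VAS, IGA and Skindex shells (14.2.3, 14.2.5 and 14.2.8) do the same.

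The model terms in SAP 4.3.1 are treatment, study site and visit, with an interaction of treatment, visit and study site. No subgroup variable enters. SAP 3.6 plans no covariate-adjusted analyses and SAP 3.7 no multiplicity adjustment. Protocol 15.4.5 says efficacy p-values are to be read as exploratory because multiple endpoints are not adjusted for.

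**The concern.** A subgroup analysis asks whether the treatment effect differs between groups. A p-value inside each group does not answer that. It reflects the effect, the group's size and chance together, and a group with fewer patients will often miss significance when the effect is the same.

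The layout invites the comparison all the same. Sex, age and race have two levels each and AD sites three, so there are nine subgroup levels. Nine levels by three visits by three scores (EASI, VAS, IGA) gives 81 within-subgroup t-test p-values before Skindex is counted. Neither document says how a difference between groups is to be interpreted. At stake is the reading of secondary and exploratory results, for example in choosing a population for a later trial. The overall comparison of B244 with vehicle is not affected.

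**Working it through.** **Inputs.** From Protocol 15.1 (repeated in SAP 3.1): "A sample size of 52 per group achieves >80% power to reject the null hypothesis of equal means", at a "significance level (alpha) of 0.025 using a one-sided two-sample equal-variance t-test", with a true difference of 3.9 EASI points (changes of -1.4 and -5.3) and SD 7.0. Allocation is 1:1, and 130 randomised less 20% dropout leaves 104, or 52 per arm. The documents give no subgroup sizes, so the splits below are assumptions. Each subgroup is taken as balanced between arms.

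**Plan's own figure.** For n per arm, the noncentrality is difference / (7.0 × √(2/n)) with 2n - 2 degrees of freedom. At n = 52 it is 3.9 / (7.0 × √(2/52)) = 2.84 on 102 df. Power is 80.3%, which agrees with the stated figure of over 80%.

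**Separate tests, same true effect in everyone.** The two groups contain different patients, so their tests are independent. With powers p and q,

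P(exactly one significant) = p(1 - q) + q(1 - p).

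At a true effect of 3.9:

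| Split | n per arm in each group | Power in each | Exactly one significant |
|---|---|---|---|
| 50/50 | 26, 26 | 0.504, 0.504 | 50% |
| 60/40 | 31, 21 | 0.579, 0.422 | 51% |
| 70/30 | 36, 16 | 0.645, 0.332 | 55% |
| 80/20 | 42, 10 | 0.713, 0.218 | 62% |

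For example, at 70/30: 0.645 × 0.668 + 0.332 × 0.355 = 0.55.

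Smaller true effects, at 50/50:
- 1.95 points: power 0.165 in each half, so 2 × 0.165 × 0.835 = 28%.
- 1.0 point: power 0.073 in each half, so 2 × 0.073 × 0.927 = 14%.
- No effect: 2 × 0.025 × 0.975 = 5%.

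These three figures barely move with the split: at 80/20 they are 29%, 13% and 5%.

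**AD sites.** With three groups and a true effect of 3.9, at least one group is significant and at least one is not in 68% of trials (equal thirds) to 74% (10/20/70).

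**All four factors together.** In 5,000 simulated trials per scenario (one endpoint, one visit, factors treated as independent, uniform effect of 3.9), at least one factor showed discordant significance in 89% to 90% of trials.

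**Interaction test instead.** In the same simulations a two-sided 0.05 interaction test gave a false signal in about 5% of trials per factor (4.7% to 5.7%), and for at least one of the four factors in about 18% to 19%.

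Its power is low. For two groups with a and b patients per arm, the SE of the difference between their effects is 7.0 × √(2/a + 2/b).
- 50/50: SE = 2.75. For a between-group difference of 3.9, 3.9 / 2.75 = 1.42 and power is 30%. The difference detectable with 80% power is 2.80 × 2.75 = 7.7 points.
- 80/20: SE = 3.48. The ratio is 1.12 and power is 20%. The detectable difference is 9.8 points.

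**The case against.** **The documents make no subgroup claim.** A reader might infer that the plan will produce, or intends, claims of differential efficacy. The documents do not support that. Safety is the primary objective, no subgroup hypothesis or decision rule is stated, Protocol 15.4.5 calls efficacy p-values exploratory, and SAP 4.3.1 labels the AD-site analysis exploratory. This stands, and it limits the point to a risk of misreading. The caveats still do not supply a between-group comparison. The Protocol's caveat is about multiple endpoints, and in the SAP only the AD-site analysis carries the exploratory label.

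**The 50% figure depends on the scenario.** This stands too. For equal halves, 2p(1 - p) peaks at p = 0.5, which is almost exactly where the planned effect puts it. Half that effect gives 28%. Unequal splits at the full effect go higher, to 62% at 80/20. The figures concern the per-visit t-tests, not the repeated-measures model, which yields p-values for treatment and interaction across visits.

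**Intervals are already planned.** Partly true. The subgroup shells carry a 95% CI for the treatment difference, but SAP 4.3.1 specifies it as one-sided, and it describes each group alone.

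**Interaction tests are weak here.** True: 20% to 30% power for a between-group difference as large as the whole planned effect. An interaction p-value alone could therefore replace one misreading with another, since non-significance might be taken as proof of a uniform effect. The estimate and its interval have to be shown and the low power stated.

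**Conclusion.** The point holds as a low-severity omission. For sex, age, race and number of AD sites, the plan reports p-values within groups and nothing that compares the effect between them. If the true effect is uniform, exactly one of two groups is significant in about 50% to 62% of trials at 3.9 points, about 28% at 1.95, about 14% at 1.0 and about 5% at no effect.

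These figures rest on 52 evaluable patients per arm, SD 7.0, the one-sided 0.025 t-test at one visit and assumed splits of 50/50 to 80/20. They show how often the discordant pattern would arise by chance, not how often anyone would draw a conclusion from it. The sample size and the overall treatment comparison are unaffected.

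**What to change.** Replace the within-subgroup tests in SAP 4.3.1 and 4.3.2 as follows, and edit the matching shells.

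- For each factor, fit one model to the ITT population for EASI change at Day 28, with treatment, subgroup and treatment-by-subgroup. Do the same for VAS, IGA and Skindex 16.
- Enter number of AD sites as a three-level factor: a joint two-degree-of-freedom interaction test, with the contrasts between levels shown.
- Report the interaction estimate with its 95% CI and p-value, and the treatment difference within each group with a two-sided 95% CI.
- Drop the within-subgroup p-values from the subgroup tables.
- State in SAP 3.8 that the subgroup results are hypothesis-generating, and that a non-significant interaction does not show homogeneity because power is only about 20% to 30% for a between-group difference of 3.9 points.

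The cost is a few lines of SAS and a table-shell edit. No new data and no change in sample size are needed.
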